2. INVESTIGATIONAL PLAN

2.1. Study Design and Randomization

This is a multicenter, open-label extension study to assess the long-term safety and efficacy of repeat doses of dupilumab in adults with moderate-to-severe AD who have previously participated in controlled studies of dupilumab or were screened for a phase 3 study (R668-AD-1334 or R668-AD-1416) but could not be randomized because of randomization closure. There is no randomization required for entry into this OLE study.

The parent studies include the following 14 studies.

- R668-AD-0914
- R668-AD-1021
- R668-AD-1026
- R668-AD-1117
- R668-AD-1121
- R668-AD-1224
- R668-AD-1307
- R668-AD-1314
- R668-AD-1334
- R668-AD-1412
- R668-AD-1415
- R668-AD-1416
- R668-AD-1424
- R668-AD-1433

2.2. Sample Size and Power Considerations

Based on the numbers of patients enrolled or screened in the antecedent dupilumab studies, it is anticipated that approximately 2500 patients will be enrolled in this global study. By then end of May2017, the study enrollment is completed. There are 2678 patients enrolled.

No formal sample size or power calculations were performed for this study.

2.3. Study Plan (Schedule of Study Assessment)

The study consists of a screening period, a treatment period and a follow-up period. The dose level, the duration of treatment period and follow-up period were modified for the study through several protocol amendments. These modifications are outlined in [Table 1](#).

Table 2: Study dose level and study duration under each protocol version

Protocol Version	Country	Dose Level (mg)	Duration of Treatment Period	Duration of Follow-up period
Original and amendment 1	Global	200	100 weeks	16 weeks
Amendment 2 and 3	Global	300	100 weeks	16 weeks
Amendment 4	Global	300	148 weeks or until commercially available	16 weeks
Amendment 5 and 6	Great Britain	300	100 weeks	16 weeks
Amendment 6	Global, Hungary, Japan	300	148 weeks or until commercially available	16 weeks
Amendment 7	Global, Hungary	300	148 weeks or until commercially available	12 weeks
Amendment 7*	France, Germany, Poland, Japan	300	Extend treatment period through approximately 31 December 2017	12 weeks
Amendment 7	Great Britain	300	100 weeks	12 weeks
Amendment 8**	Poland, Finland	300	Extend treatment period to up to 5 years (week 260)	12 weeks
Amendment 8**	France	300	Extend treatment period to approximately September 2018	12 weeks

* Note: Under protocol amendment 7 for France, Germany, Poland and Japan, patients who had already completed the End of Treatment visit under protocol amendment 6 were permitted to resume treatment with study drug. Patients who had completed the End of Study visit were permitted to re-enter the study. The treatment period ended for all patients in these countries on or about 31 December 2017.

** Note: Patients in Poland, Finland and France who had completed their End of Treatment/End of Study visit as per amendment 7 were permitted to resume treatment/re-enter the study provided that no more than 12 weeks had elapsed since their End of Study visit. The duration of the overall treatment period for patients in Poland and Finland was extended to 5 years, and to September 2018 for patients in France.

The study flow diagrams under protocol amendment 7 and 8 are provided in [Figure 2](#), [Figure 3](#), [Figure 34](#) and [Figure 35](#) below:

Under protocol amendment 6, the planned study duration was up to three years or until dupilumab became commercially available in the geographic region of the patient. Protocol amendment 7 was adopted in order to permit those patients in France, Germany, Poland and Japan who had already completed three years of treatment to either continue or re-start treatment through 31 December 2017. Patients who were in the 16-week safety follow-up period were permitted to resume treatment. Patients who had an End of Study visit were permitted to re-enter the study after being re-consented. Patients who had completed 3 years of treatment resumed treatment in a newly created series of visits called the “treatment extension” period. All patients were scheduled to have an End of Treatment visit on or around 31 December 2017.

Protocol amendment 8 extended the treatment period for up to 5 years for patients in Poland and Finland and to September 2018 in France. Again, patients who had previously had an End of Treatment visit under Amendment 7 and were in the 12-week safety follow-up period were permitted to resume treatment. Patients who had an End of Study visit were permitted to re-enter the study after being re-consented. This is illustrated in Figure 1.

As a consequence of these two amendments, certain patients from these countries experienced gaps in treatment. One gap occurred between the Amendment 6 end of treatment (EoT) date and resumption of treatment under Amendment 7 for approximately 113 patients with a median duration of gap around 17 weeks and maximum duration of around 33 weeks. In addition, there are approximately 272 patients from Poland, Finland and France who experienced a second treatment gap from the EoT date under Amendment 7 and resumption of treatment under Amendment 8 with a median duration of gap around 10 weeks and maximum duration of around 21 weeks.

Figure 1: Overall Study Flow Diagram Showing the Treatment Gap due to Protocol Amendment 7 and 8

[figure not shown]
[figure not shown]

Figure 2: Study Flow Diagram for Protocol Amendment 7 (Global)

^a Patients who fail screening or who fail to complete the baseline visit within 28 days of screening may be rescreened upon approval by the medical monitor.

[figure not shown]
^b A loading dose of 600 mg SC (two 300 mg doses administered on the same day) dupilumab will be administered on day 1 unless the patient has received a dose of dupilumab in the 4 weeks prior to baseline. If the patient has received a dose of dupilumab in the past 4 weeks, then they will receive a single 300 mg dose at baseline. The first dose should be at least 1 week after the last dose in the previous study, and then 300 mg dupilumab qw starting on day 8.

^c Patients will be monitored at the study site for a minimum of 30 minutes at the baseline visit.

^d Visits 10, 12, 14, and 16 have been removed per amendment 6. This yields a schedule in which visits are 8 weeks apart from week 16 through week 48. The week 48 visit is followed by a visit at 52 weeks, then visits occur every 8 weeks thereafter up to and including the End of Treatment visit (week 148).

^e Visits 3, 4, 5, and 7 were removed per amendment 6.

Figure 3: Study Flow Diagram for Protocol Amendment 7 (UK)

^a Patients who fail screening or who fail to complete the baseline visit within 28 days of screening may be rescreened upon approval by the medical monitor.

[figure not shown]
^b A loading dose of 600 mg SC (two 300 mg doses administered on the same day) dupilumab will be administered on day 1 unless the patient has received a dose of dupilumab in the 4 weeks prior to baseline. If the patient has received a dose of dupilumab in the past 4 weeks, then they will receive a single 300 mg dose at baseline. The first dose should be at least 1 week after the last dose in the previous study, and then 300 mg dupilumab qw starting on day 8.

^c Patients will be monitored at the study site for a minimum of 30 minutes at the baseline visit.

^d Visits 10, 12, 14, and 16 have been removed per amendment 6. This yields a schedule in which visits are 8 weeks apart from week 16 through week 48. The week 48 visit is followed by a visit at 52 weeks. Visits from 60 weeks through the EOT visit occur every 8 weeks.

^e Visits 3, 4, 5, and 7 were removed per amendment 6.

Figure 4: Study Flow Diagram for Protocol Amendment 7 (France, Germany, Poland, Japan)

^a Patients who fail screening or who fail to complete the baseline visit within 28 days of screening may be rescreened upon approval by the medical monitor.

^b A loading dose of 600 mg SC (two 300 mg doses administered on the same day) dupilumab will be administered on day 1 unless the patient has received a dose of dupilumab in the 4 weeks prior to baseline. If the patient has received a dose of dupilumab in the past 4 weeks, then they will receive a single 300 mg dose at baseline. The first dose should be at least 1 week after the last dose in the previous study, and then 300 mg dupilumab qw starting on day 8.

^c Patients will be monitored at the study site for a minimum of 30 minutes at the baseline visit.

^d Visits 10, 12, 14, and 16 have been removed per amendment 6. This yields a schedule in which visits are 8 weeks apart from week 16 through week 48. The week 48 visit is followed by a visit at 52 weeks, then visits occur every 8 weeks thereafter up to and including the End of Treatment visit (week 148).

^e Visits 3, 4, 5, and 7 were removed per amendment 6.

^f Patients who have completed their End of Study (EOS) visit and are resuming treatment per Amendment 7 may re-enter the trial at visit 31 after the trial re-entry visit. Patients who have completed their End of Treatment (EOT) visit may resume treatment at visit 31.

^g All patients will be scheduled for an EOT visit on or about 31 December 2017.

Figure 5: Study Flow Diagram for Protocol Amendment 8 (Poland, Finland)

Screening		Treatment Period ^{b, c}									
	Baseline										
V1 D-28 to D- 1 ^a	V2 D1	V3 ^e W1	V4 ^e W2	V5 ^e W3	V6 W4	V7 ^e W8	V8 W12	V9-V30 ^d W16- W148 (every 8 weeks)	V31 ^{f, g} -V43 (every 8 weeks)	V44/EOT ^g	EOS 12 weeks after last dose

^a Patients who fail screening or who fail to complete the baseline visit within 28 days of screening may be rescreened upon approval by the medical monitor.

^b A loading dose of 600 mg SC (two 300 mg doses administered on the same day) dupilumab will be administered on day 1 unless the patient has received a dose of dupilumab in the 4 weeks prior to baseline. If the patient has received a dose of dupilumab in the past 4 weeks, then they will receive a single 300 mg dose at baseline. The first dose should be at least 1 week after the last dose in the previous study, and then 300 mg dupilumab qw starting on day 8.

^c Patients will be monitored at the study site for a minimum of 30 minutes at the baseline visit.

^d Visits 10, 12, 14, and 16 have been removed per amendment 6. This yields a schedule in which visits are 8 weeks apart from week 16 through week 48. The week 48 visit is followed by a visit at 52 weeks; then visits occur every 8 weeks thereafter up to and including the End of Treatment visit).

^e Visits 3, 4, 5, and 7 were removed per amendment 6.

^f Patients who have completed their end of treatment (EOT) visit as per amendment 7 may resume treatment with study drug at the next scheduled visit they would have attended if they had not had an EOT visit.

^g Patients who have completed their End of Study (EOS) visit as per amendment 7 will be re-evaluated for eligibility at a trial Re-Entry visit. Patients eligible to re-enter the trial may resume treatment at the next scheduled visit they would have attended if they had not completed the study. Patients are not eligible to re-enter the trial if more than 12 weeks have elapsed since their End of Study visit.

The Schedule of Events table for global protocol amendment 7 and protocol amendment 8 for Poland/Finland is presented in [Appendix 10.2](#).

After providing informed consent, patients will be assessed for study eligibility at the screening visit. The screening visit in this study may coincide with the last visit in the previous study, in which case assessments that are common to both studies will be performed only once.

In the original protocol and protocol amendment 1, it stated that “Patients enrolled in this study will receive weekly doses of 200 mg subcutaneous (SC) dupilumab. A loading dose of 400 mg dupilumab (200 mg initial dose, followed by a 200 mg loading dose) will be administered on day 1 (unless last dose administered in the previous AD study is less than 4 weeks before their first dose in the current study, in which case they will receive 200 mg dupilumab), which will allow systemic concentrations to reach steady state faster, and potentially reduce the time to clinical effect.”

Starting from protocol amendment 2, eligible patients received a 600 mg SC dupilumab loading dose (300 mg initial dose, followed by a 300 mg loading dose) on day 1 (unless the last dose administered in the previous dupilumab AD study was less than 4 weeks before their first dose in the current study, in which case they received 300 mg dupilumab; the first dose of 300 mg should be at least 1 week after the last dose in the previous dupilumab study), and then 300 mg SC dupilumab qw starting on day 8. Patients returned for visits as specified in the schedule of events according to the most current protocol amendment for their geographic region.

Patients and/or caregivers who were willing and able to administer dupilumab doses outside the clinic were trained on injecting study drug unless they had already been trained during their participation in the previous study. These patients self-injected study drug (or had the drug administered by a caregiver) during weeks in which no clinic visit was scheduled. Safety, laboratory, and clinical assessments were performed at specified clinic visits.

Patients who received treatment with a prohibited or restricted medication were to be discontinued from study drug for the duration of the prohibited treatment (plus 5 half-lives, as applicable). Study treatment could be resumed in consultation with the medical monitor.

Patients who tested positive for ADA at their last study visit (early termination or end of study) may be asked to return to the clinic to have additional ADA samples collected for analysis.

Samples for clinical chemistry and hematology, drug concentrations and anti-drug antibodies (ADAs) were collected at various time points throughout the study according to the protocol. One sample for DNA analysis was collected from patients who consented to participate in the optional genomic sub-study.

3. ANALYSIS POPULATIONS

In accordance with guidance from the International Conference of Harmonization of Technical Requirements for Registration of Pharmaceuticals for Human Use (ICH) guideline ICH E9 Statistical Principles for Clinical Trials (1998), the following populations will be used for all statistical analyses:

3.1. The Safety Analysis Set (SAF)

The safety analysis set (SAF) consists of all patients who received any study drug. Efficacy, treatment compliance/administration, and all clinical safety variables will be analyzed using the SAF.

3.2. The Pharmacokinetic Analysis Set (PKAS)

The PK analysis set consists of all treated patients who had at least one non-missing drug concentrations result following the first dose of study drug.

3.3. The Anti-Drug Antibody (ADA) Analysis Set (AAS) and Neutralizing Antibody (NAb) Analysis Set (NAS)

The ADA population consists of all treated patients who received any study drug and who had at least one non-missing ADA result after the first dose of the study drug.

The neutralizing antibody (NAb) Analysis Set (NAS) consists of all patients who received any study drug and who had at least one non-missing Nab result or who had all samples negative in the ADA assay after first dose of the study drug.

4. ANALYSIS VARIABLES

4.1. Demographic and Baseline Characteristics in Current Study

The following demographic and baseline characteristics variables in current study will be summarized:

- Demographic variables:
 - Age (year)
 - Age group (≥ 18 -<40 year, ≥ 40 -<65 year, ≥ 65 year) and elder group (≥ 65 - <75 year, ≥ 75 - <85 year; ≥ 85 year)
 - Sex (Male, Female)
 - Ethnicity (Hispanic or Latino, Not-Hispanic or Latino)
 - Race (White, Black or African American, Asian, Other)
 - Baseline Weight (kg)
 - Baseline weight group (<70 kg, ≥ 70 -<100 kg, ≥ 100 kg)
 - Baseline Height (cm)
 - BMI (kg/m^2)
 - BMI group (kg/m^2) (<15, ≥ 15 -<25, ≥ 25 -<30, ≥ 30)
- Baseline characteristics in current study:
 - Previous AD study number
 - Duration of AD at Day 1 of current study (< 26 years, ≥ 26 years)
 - Previous treatment received in the parent study (placebo, dupilumab)
 - Previous dupilumab dose received in the parent study
 - Pruritus numerical rating scale (NRS)
 - Investigator's Global Assessment (IGA) score
 - Eczema Area and Severity Index (EASI) score
 - Patient global assessment of disease status
 - Patient Oriented Eczema Measure (POEM)
 - Dermatology Life Quality Index (DLQI)
 - EQ-5D
 - Country
 - Geographic region

4.2. Characteristics of Patient Status in Parent Studies

The following variables summarizing baseline disease characteristics in the parent study are defined:

1. Baseline disease characteristics in parent study
 - Investigator's Global Assessment (IGA) score
 - Eczema Area and Severity Index (EASI) score
 - Pruritus NRS
 - Patient global assessment of disease status
 - Patient Oriented Eczema Measure (POEM)
 - Dermatology Life Quality Index (DLQI)
 - EQ-5D

The baseline value of a patient in the parent study, which is defined as the last non-missing value on or before the first dose date in the parent study, will be derived and summarized for all efficacy assessments. If a patient participated in more than one study before enrolling into AD-1225 study, the baseline value of the earliest parent study will be used and summarized. For example, for a patient who entered from AD-1415 (SOLO-CONTINUE) study, the baseline value of the patient in the parent study is the baseline value in the SOLO studies (either AD-1334 or AD-1416) in which the patient participated before rollover into the AD-1415 study.

2. The following variables for patient status at the end of treatment visit in the parent study (defined as the scheduled end of treatment visit in the parent study protocol [e.g., Week 16 for a parent study with a 16-week treatment period]) will be derived and summarized:

Number and percentage of patients:

- Achieving IGA 0 or 1
- Achieving EASI-75 ($\geq 75\%$ reduction in EASI scores from baseline of the parent study)
- Achieving EASI-50 ($\geq 50\%$ reduction in EASI scores from baseline of the parent study)
- Achieving EASI-90 ($\geq 90\%$ reduction in EASI scores from baseline of the parent study)
- Achieving improvement (reduction) of pruritus NRS ≥ 4 from baseline of the parent study
- Achieving improvement (reduction) of pruritus NRS ≥ 3 from baseline of the parent study

Patients with a missing value at end of treatment visit in the parent study after censoring for rescue treatment use or study withdrawal will be counted as non-responders at the end of treatment visit in the parent study. For patients who had been screened for a phase 3 study (R668-AD-1334 or R668-AD-1416) but could not be randomized because of randomization closure, the patient's status at end of treatment visit in the parent study will be blank. For patients from the 4-week treatment period of phase I or II studies (i.e. R668-AD-0914, R668-AD-1026 and R668-AD-1121), the patient's status at end of treatment visit in the parent study will be blank, since most patients have shown non-response to treatment after a treatment duration of only 4 weeks.

3. The treatment gap between the date of the last dose of dupilumab in the parent study and the first dose date in the current study will be derived and summarized by the following categories: ≤ 8 weeks, > 13 weeks.
4. The following variables for patients' exposure to dupilumab in the parent study will be provided:
 - Cumulative dupilumab dose (mg) in the parent study. For patients who participated in more than one parent study (e.g. patients enrolled in R668-AD-1415 study who previously participated in R668-AD-1334 or R66-AD-1416 study) the cumulative dupilumab dose in parent study is the sum of all dupilumab doses received in all parent studies.
 - Duration of treatment of dupilumab (in weeks) in the parent study, defined as date of last dupilumab injection – date of first study drug injection) + 7]/7. The duration will be categorized by ≤ 4 weeks (ie. 28 days), 5- ≤ 12 weeks, 13- ≤ 16 weeks 17- ≤ 24 weeks, 25- ≤ 52 weeks and > 52 weeks.

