- Gender (Male, Female)
- Race (White, Black or African American, Asian, Others)
- Ethnicity: Hispanic or Latino (yes/no)
- Previous usage of ciclosporin (CsA) (Yes, No)
- Previous usage of methotrexate (MTX) (Yes, No)
- Previous usage of Azathioprine (Aza) (Yes, No)
- Previous use of systemic immunosuppressants for AD (Yes, No)
- History of asthma (Yes, No)
- History of nasal polys (Yes, No)
- History of allergic rhinitis (Yes, No)
- History of food allergies (Yes, No)
- Previous treatment of dupilumab in parent study (Yes, No)
 - For patients who received dupilumab in parent study, data from the following two subgroups will also be summarized.
 - Re-treatment (treatment gap > 8 weeks): – Patients who came from the dupilumab arms of parent studies, and if the gap period between the last dupilumab study drug injection in parent study and the first study drug injection in current study is > 8 weeks (greater than 64 days).
 - Continuous treatment (gap ≤ 8 weeks) – patients who came from the dupilumab arms of parent studies, and if the gap period between the last dupilumab study drug injection in parent study and the first study drug injection in current study is ≤ 8 weeks (less than or equal to 64 days).

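### SAP 4.2 leaves parent-study gaps of more than 8 and up to 13 weeks, and some exposure durations, without a category, and blanks response for three 4-week studies because of the result seen

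*SAP*

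**What the plan says.** SAP 4.2 sets out four groups of parent-study variables. Three of its rules matter here.

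- **Gap before entry (item 3).** The time from the last parent-study dupilumab dose to the first dose in this study "will be derived and summarized by the following categories: ≤ 8 weeks, > 13 weeks". No other category is named.
- **Parent exposure (item 4).** Duration in weeks is "defined as date of last dupilumab injection – date of first study drug injection) + 7]/7". The categories follow: "The duration will be categorized by ≤ 4 weeks (ie. 28 days), 5- ≤ 12 weeks", then "13- ≤ 16 weeks 17- ≤ 24 weeks, 25- ≤ 52 weeks and > 52 weeks". No rounding rule is given.
- **End-of-treatment status (item 2).** Response is taken at each parent study's own scheduled end-of-treatment visit. Patients with a missing value there, after censoring for rescue or withdrawal, "will be counted as non-responders at the end of treatment visit in the parent study". For patients from R668-AD-0914, R668-AD-1026 and R668-AD-1121 the status is left blank, "since most patients have shown non-response to treatment after a treatment duration of only 4 weeks". It is also blank for patients who were screened for a phase 3 study but never randomized.

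SAP 5.7 uses the same gap for an efficacy subgroup. One arm opens "Re-treatment (treatment gap > 8 weeks" and is put in days as more than 64; the other is 8 weeks or less, put as 64 days or less.

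**The concern.** Categories in a summary table should cover every value the variable can take. Otherwise rows do not add up to the analysis set, or each programmer closes the holes differently. Here the gap list jumps from 8 to 13 weeks, and the exposure list puts whole-week lower limits on a variable that moves in steps of one seventh of a week.

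The blanking rule is a separate matter. Never-randomized patients had no parent treatment, so a blank is natural for them. The patients of the three 4-week studies were treated, and the stated ground for blanking them includes how they responded. A rule that depends on the outcome sits badly beside a non-responder rule in the same paragraph.

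At stake is the description of prior exposure, interval off drug and earlier response. That is background to the secondary objective on immunogenicity in the context of re-treatment (protocol 2.2). No primary or key secondary endpoint depends on these tables.

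**Working it through.** The plan states no figure to reproduce, so the check is to test each whole-day value against the stated categories.

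**Gap.** With g in days, the rows are g/7 ≤ 8 and g/7 > 13. Since 8 × 7 = 56 and 13 × 7 = 91, the uncovered values are g = 57 to 91, which is 91 − 57 + 1 = 35 day values. If the 64-day reading of SAP 5.7 is carried into 4.2, the uncovered values are 65 to 91, which is 27.

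Set beside SAP 5.7:

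| Gap (days) | SAP 4.2 row | SAP 5.7, by weeks | SAP 5.7, by days |
|---|---|---|---|
| up to 56 | ≤ 8 weeks | continuous | continuous |
| 57-64 | none | re-treatment | continuous |
| 65-91 | none | re-treatment | re-treatment |
| 92 or more | > 13 weeks | re-treatment | re-treatment |

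**Exposure.** Let D = (last injection − first injection) + 7 in days, and weeks = D/7, unrounded.

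| Cut-point | D at cut-point | Uncovered D | In weeks |
|---|---|---|---|
| 4 weeks | 28 | 29-34 | 4.14-4.86 |
| 12 weeks | 84 | 85-90 | 12.14-12.86 |
| 16 weeks | 112 | 113-118 | 16.14-16.86 |
| 24 weeks | 168 | 169-174 | 24.14-24.86 |
| 52 weeks | 364 | none (365 falls in > 52) | - |

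That is 4 × 6 = 24 uncovered day values.

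**Effect of rounding.** Rounding up to whole weeks closes all four holes and agrees with the SAP's own equation of 4 weeks with 28 days: D = 29 becomes 5 weeks. Rounding down or to the nearest week also closes them, but puts D = 29 in the ≤ 4-week row, against that equation. Rounding to one decimal leaves all four open. The same patient can therefore land in different rows under rules that the SAP does not choose between.

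**Can real schedules reach a hole?** Protocol 1.2.2 describes a 16-week phase 2b study with weekly, 2-weekly and 4-weekly regimens. Assume that the last planned dose falls one dosing interval before the end and may shift by up to 3 days.

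- Weekly: last − first = 105, D = 112, 16.0 weeks. One to three days late gives 16.14 to 16.43: uncovered.
- 2-weekly: last − first = 98, D = 105, 15.0 weeks. No shift of up to 3 days reaches a hole.
- 4-weekly: last − first = 84, D = 91, 13.0 weeks. One to three days early gives 12.86 to 12.57: uncovered.

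**Blanked status.** Let N patients have a status, R of them responders, and let B be blanked, r of whom responded. With everyone's observed status the proportion is (R + r)/(N + B).

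- Blanks out of the denominator: R/N, which is higher than the full figure only if r/B < R/N.
- Blanks kept in the denominator: R/(N + B), which cannot exceed the full figure.

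SAP 5.1.2 summarizes this status for all patients in the safety set, and 4.2 does not say whether blanks stay in the denominator. The direction is therefore open, and the documents give none of N, R, B or r.

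**The case against.** The strongest reply is that little is lost. SAP 5.1.2 lists the off-treatment period in days and the duration of parent exposure for the whole safety set, so a patient with a 10-week gap lacks a category row but stays in the analysis. That stands. A reader might infer that these patients disappear from the parent-study tables; the documents do not support it, since their parent baseline data and these duration summaries remain.

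A reader might also infer that these tables decide who counts as re-treated. SAP 5.7 does that, with a split that omits nobody, apart from its 64-day inconsistency.

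On exposure, whole-week labels and the 28-day note may mean that weeks were to be rounded up. That is plausible and would close the holes, but the SAP does not say so. On the gap, a list that jumps from 8 to 13 weeks may have lost a middle entry in the PDF text. That cannot be settled without the approved page.

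On blanking, the SAP's reason also mentions the short treatment, which is a comparability argument. It carries some weight, but the rule already takes status at each study's own end-of-treatment visit, and a separate row would meet the same worry openly. It is also fair that SAP version 2.0 dropped the subgroups by parent end-of-treatment response (Table 1 of the SAP), so little now rests on this variable.

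**Conclusion.** The point holds as a narrow correction to descriptive tables. On the text as it stands, 35 day values of the gap and 24 day values of exposure have no category. SAP 5.7 contradicts itself for gaps of 57 to 64 days. End-of-treatment status is handled in two ways in one paragraph, one of them tied to the observed result.

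This rests on two conditions: that no middle gap category was lost from the page, and that weeks are used unrounded.

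Two stronger readings go too far. One is that a sizeable share of parent-study completers falls into the exposure holes. The documents give no distribution of gaps or durations, and whether a small shift in the last dose matters depends on the regimen. They also name only 4 and 16 weeks as parent treatment lengths, so the holes cannot be said to lie above every planned length.

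The other is that blanking overstates response at entry. The direction depends on an unstated denominator. Status at entry is the current-study baseline IGA, EASI and pruritus NRS (SAP 4.1 and 5.1.1), which is not blanked.

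**What to change.** 1. Check the approved SAP page for a middle gap category lost from the text.
2. State the gap as ≤ 8, > 8 to ≤ 13, and > 13 weeks.
3. State parent exposure as ≤ 4, > 4 to ≤ 12, > 12 to ≤ 16, > 16 to ≤ 24, > 24 to ≤ 52, and > 52 weeks. This leaves no uncovered day and keeps 28 days as the first limit.
4. In SAP 5.7, reconcile 64 days with 8 weeks (56 days), and use the same day limit in 4.2.
5. Show observed end-of-treatment status for the three 4-week studies as a separate row, and state the denominator for each percentage, including how never-randomized patients are treated.

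The cost is SAP wording and the matching table programs. No new data are needed and no endpoint changes.
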